1.0 Research Design

1.1 Purpose/Specific Aims

The overall purpose of the study is to test the effect of metformin on exercise intensity based training adaptations in adults with metabolic syndrome.

A. Objectives

Understand effect of metformin on training intensity mediated vascular versus metabolic insulin sensitivity in adults with metabolic syndrome for clinical health.

B. Hypotheses / Research Question(s)

The overarching hypothesis is that metformin may blunt adaptation following high intensity exercise by lowering/attenuating oxidative stress. Thus, compared with high intensity exercise plus metformin, low intensity exercise plus metformin will produce greater vascular insulin sensitivity and metabolic insulin sensitivity changes following 16 weeks of treatment. In addition, we anticipate that high intensity exercise based training alone will produce greater effects than low intensity exercise. Lastly, we hypothesize that these changes in metabolic and vascular insulin sensitivity will correlate with glycemic control and blood pressure changes.

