1.2 Research Significance

Metabolic Syndrome (MetS) is associated with a 3-fold cardiovascular disease (CVD) mortality risk compared with healthy controls, and it is estimated that 40% of the U.S. will have MetS by 2020 (1). MetS is characterized by elevated blood glucose, hypertension, carotid artery thickness, dyslipidemia, and obesity (2). Although skeletal muscle insulin resistance is an important underlying cause of MetS, vascular insulin resistance, particularly at the microvasculature level, may actually contribute to the pathogenesis of metabolic insulin resistance and drive the CV complications in type 2 diabetes (T2D) (3). Here we propose that vascular insulin resistance is central to CVD risk reduction in MetS and interventions are needed that target enhancing endothelial function and decreasing arterial stiffness. High intensity exercise (HiEx) is an established treatment to reduce CVD risk in MetS patients (4-7) by, in part, improving basal endothelial function and arterial stiffness (8-10), although this has not tested under insulin-stimulated conditions. Metformin is a 1st line agent to treat hyperglycemia due to in part to its ability to reduce hepatic glucose output, and protect against CV morbidity and mortality as evidenced by the UKPDS (11). Surprisingly, our preliminary work in MetS/prediabetic individuals shows that metformin may ameliorate CVD risk, but when combined with HiEx there tends to be a blunting effect on skeletal muscle metabolic insulin resistance (12). One attractive alternative to promote vascular and metabolic adaptation, and test the additive effects of metformin on exercise, is to prescribe exercise that does not primarily rely on mitochondrial oxidative stress to induce adaptation, i.e. low intensity exercise. Herein, we propose that metformin may interact with exercise in an intensity based manner for adaptations related to skeletal muscle metabolic and/or vascular insulin resistance. These findings will have direct impact on public health for glycemic control and blood pressure regulation as well as inform how metformin interacts with physical activity behavior.

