Blood pressure:

 Subjects blood pressure will be taken at the beginning of each testing visit. This test takes about 5 minutes.

Large artery flow-mediated dilation (FMD):

• This test allows us to measure the blood flow through the subjects arteries.

12/31/2499

- This procedure uses an ultrasound device to measure blood flow in an artery in the subjects upper arm and leg. Ultrasound is a diagnostic procedure that creates a picture image using sound waves. Unlike X-rays, ultrasound does not involve radiation.
- Just prior to the test subjects will be asked to lie down on a bed quietly for 20 minutes. During this time, subjects will have blood pressure taken, and subjects will be connected to an electrocardiogram (ECG) that will monitor your heart rate. After the 20 minutes have passed, an ultrasound probe will be lightly pressed against the inside of the subjects upper arm and leg.
- Next we will place a blood pressure cuff on the subjects forearm only and pump it up tightly. This
 portion of the test may cause some discomfort in their forearm and fingers (such as pain, tingling,
 and numbness).
- We will keep the cuff inflated for 5 minutes, take images, then release it, and measure the increase in blood flow in one of the arteries in your upper arm using the ultrasound probe.
- This procedure takes about 15 minutes. We will perform this procedure just before the glucose beverage during the OGTT, and then again at 1, and 2 hours after you drink the glucose beverage.
 For the clamp test, we will perform blood flow measures once at the beginning and once at the end.

Common carotid artery intima-media thickness (CCA-IMT)

- This test allows us to measure the level of blood vessel thickness in the artery.
- This procedure uses an ultrasound device, similar to FMD above, to measure degree of vascular tissue thickness between the inner 2 layers of the vessel wall in an artery of the upper neck. Ultrasound is a procedure that creates a picture image using sound waves. Unlike X-rays, ultrasound does not involve radiation.
- This procedure takes about 15-20 minutes.
- Prior to the test the subject will be asked to lie down on a bed quietly for about 15 minutes. During
 this time, blood pressure will be taken, and the subject will be connected to an electrocardiogram
 (ECG) that will monitor heart rate. Then an ultrasound probe will be lightly pressed against the
 subjects neck. Images will be taken for about 5 minutes.

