- This will take about 10 minutes and will occur before and after the 2 hour clamp technique during.

RANDOMIZATION and STUDY PROCEDURES

Subjects will be randomly assigned (like the flip of a coin) to 1 of 4 study treatment groups. Subjects have an equal chance of being assigned to any one of the groups. Neither the subject nor their doctor can choose which treatment they are assigned. Neither subject nor their doctor will know which study treatment they will get until the study is done. If the subjects doctor needs to know whether metformin or placebo pill is prescribed due to medical reasons that directly affects medical care of the subject, the people doing this study can find out.

PHASE 3: INTEREVENTION PERIOD (Visits 5-53)

Ambulatory Blood Pressure:

- This is used to look at blood pressure throughout the entire day and night for 24 hours.
- This measure occurs using a blood pressure cuff that is wrapped around the subjects arm with a holter monitor secured to their belt that contains a battery and recording device.
- Subjects are instructed to go about their normal activities throughout the day.
- During periods of inflation and deflation, we ask subjects to relax their arm.
- This test will occur before the first training session.
- At the same time, subjects will be given standardized meals to follow for the 24-hr collection period before and after the intervention.

The Ambulatory Blood Pressure will occur before the intervention period and within the last week of the intervention.

Prior to the intervention subjects will be randomized (like the flip of a coin) to receive 1 of 4 treatment options for 16 weeks – all of which expend a matched number of calories per week. *Note, due to COVID-19 if supervised exercise sessions need to vary for safety reasons, virtual sessions will be established within reason to maintain "supervised" sessions.*

- Low Intensity Exercise Training (LoEx) + Placebo
- High Intensity Exercise Training (HiEx) + Placebo
- LoEx + Metformin
- HiEx + Metformin

 $\underline{\textit{LoEx} + \textit{Placebo}}$: If subjects are randomly assigned to this group, subjects will participate in exercise training. Subjects will be asked to attend 3 regularly supervised and scheduled training sessions (e.g. M,

12/31/2499

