 - Subjects will be required to wear clothes without metal on them (including zippers and bras with an underwire). If clothes have metal, we will ask that subjects change into a pair of shorts and a t-shirt or wear a lab hospital gown.
 - If there are technical issues with the DEXA machine we will measure the total amount of fat and muscle in the subjects body with the BodPod® in the IFNH.
 - We will provide a swimsuit and swim cap for subjects to wear during this procedure to help standardize the results. The swimsuit and swim cap are provided to get accurate results. Subjects will not get wet at any time during this test. Subjects will enter the device and sit down. A door will close while the subject sits in the BodPod®. They are asked to breath normal and be still. The BodPod® looks like a large white egg with a window on the door.

NOTE: in the event of scheduling conflicts, cardiovascular fitness and/or body composition assessments may be completed within 1 week of doing the OGTT during Visit 58.

END OF STUDY:

After subjects have completed Phase 5, the study will be complete.

B. Data Points

We are collecting blood and urine during experimental visits. Vital signs, including blood pressure, temperature, heart rate, as well as aerobic fitness, body composition, resting metabolism, non-exercise physical activity, appetite, as well as quality of life. Please see the study overview (Study Duration) that outlines when outcomes will be collected.

C. Study Duration

Subjects participation in this study will require about **58** study visits over about 7-8 months. Each visit will last between **1-6** hours depending on whether it is for research purposes (e.g. about 3-6 hours) or exercise training (e.g. 1-1.5 hours). There are 2 Screening Visits and 5 Test Visits. Thus, the majority of visits include exercise training (48 visits).

D. Endpoints

The primary outcome for this study will be changes of basal FMD before the insulin clamp pre and post intervention. We will also examine the influence of insulin on FMD as well as metabolic insulin sensitivity, defined as the glucose infusion during the last approximate 30 minutes of the clamp procedure. Together, these findings will help tease out vasculature vs. metabolic insulin sensitivity differences between treatments. Correlations will be conducted to understand the relationship between endothelial function and metabolic insulin sensitivity with substrate oxidation,

12/31/2499

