1.5 Sample Size Justification

The primary outcome for this study will be changes of basal flow mediated dilation (FMD) before the insulin clamp pre and post intervention. Based on our prior work 47, with 15 subjects per treatment arm we expect to have at least an 80% chance of rejecting the null hypothesis that the mean pre to post-exercise change in FMD is the same for any pair of treatments if the true means of the underlying distributions differ by more than 4.2%. Details: In computing the minimum detectable effect size of 4.2%, we assumed that the measurements for pre to post-treatment change in FMD will be normally distributed and that the measurement variability in the pre to postexercise FMD changes is the same regardless of the treatment. Moreover, we assumed that the standard deviation of the underlying distributions is 3.4% based on our prior work 47, which is notably larger than reported in the metformin literature 48. To account for a total of 6 pairwise between-treatment comparisons, a Bonferroni corrected experiment-wise type I error of 0.05 was utilized to derive the minimum detectable between-treatment difference of 4.2%. Limitations: We do not have data from the literature or from our own studies with exercise to estimate power on changes in MBV, nor with the combination of exercise+metformin. However, considering MBV, we based our estimate of sample size on our study examining the effect of insulin on MBV in both skeletal and cardiac muscle in the control setting and in the setting of elevated plasma FFA. We observed that insulin significantly increased microvascular blood volume (MBV) at both sites (p<0.01) in the absence of elevated FFA and this effect was entirely blocked by elevating plasma FFA. These observations were made in 22 subjects, although less would have yielded significance ^{36, 42}. Moreover, previous work that we conducted with HiEx+metformin demonstrated significant blunting effects on systolic blood pressure vs. exercise alone with only 8 people per group 5. Anticipated dropout: Based on our prior work with this study population, we anticipate that the study participant dropout rate will be 10-15%. Therefore, we intend to enroll 80 subjects with 20 subjects randomized to each treatment intervention.

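### Does the missing formula for insulin's effect on FMD leave the vascular half of the hypothesis undefined?

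*Combined protocol and SAP*

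**What the plan says.** The hypothesis in section 1.1 B sets the two metformin arms against each other and expects the low intensity one to do better: "low intensity exercise plus metformin will produce greater vascular insulin sensitivity and metabolic insulin sensitivity changes following 16 weeks of treatment". Section 1.3 D makes the pre-to-post change in basal FMD, taken before the clamp, the primary outcome. It then adds: "We will also examine the influence of insulin on FMD as well as metabolic insulin sensitivity". The metabolic measure is tied there to glucose infusion over roughly the final half hour of the clamp. The vascular measure has no formula.

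On measurement, the FMD part of section 1.3 A says: "For the clamp test, we will perform blood flow measures once at the beginning and once at the end". Contrast-enhanced ultrasound of the microvasculature "will occur before and after the 2 hour clamp technique".

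On analysis, section 1.6 specifies a two-way repeated measures ANOVA with factors group and test, Bonferroni post-hoc comparisons and P<0.05. It applies the same approach to secondary outcomes. Section 1.8 uses the word test for pre or post and lists it apart from the within-visit time point.

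Section 1.5 powers the primary outcome only. It assumes that "the standard deviation of the underlying distributions is 3.4" percent, with 15 subjects per arm and a detectable difference of 4.2%. On multiplicity it says: "To account for a total of 6 pairwise between-treatment comparisons".

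**The concern.** Each subject has four clamp FMD values: two visits by two clamp stages. A group-by-test model takes one value per visit, and no section says which. Section 1.3 D suggests the rise during the clamp. Section 1.2 says of earlier exercise work on basal endothelial function and arterial stiffness "although this has not tested under insulin-stimulated conditions", which could suggest the end-clamp value itself. The same section stresses vascular insulin resistance "particularly at the microvasculature level", which would bring in the ultrasound measure as a third candidate.

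The choice could matter. End-clamp FMD carries the basal change inside it, so a purely basal benefit would look like a gain in vascular insulin sensitivity. The increment falls when basal FMD rises and end-clamp FMD does not, so a basal benefit could look like a loss. If the reading were chosen after seeing the data, either conclusion on half of the hypothesis could be reported as planned.

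A second worry is that section 1.1 B joins the two measures with an and, without saying whether both must succeed.

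**Working it through.** **Inputs from section 1.5.** 15 per arm; SD of the pre-to-post FMD change 3.4 points; difference 4.2 points; six pairs, so alpha = 0.05/6 = 0.0083 per pair (two-sided assumed).

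**The plan's own figure.** By the normal approximation, n = 2 × (2.638 + 0.842)² × (3.4/4.2)² = 15.9, so 16 per arm against 15 stated. At 15 per arm, power for 4.2 points is 77% (normal), 74% (t with pooled four-arm error, 56 df) or 70% (two-sample t, 28 df). This is close to the plan's claim and concerns basal FMD only. The rest uses the 28-df t-test.

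**How the two readings relate.** Let A be the pre-to-post change in end-clamp FMD and B the change in (end minus start). Then

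B = (end_post − start_post) − (end_pre − start_pre) = A − (change in basal FMD).

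Between any two arms, the contrast in B equals the contrast in A minus the contrast in the primary outcome. The readings coincide only if the arms do not differ in basal change. With a basal contrast of 4.2 points, any A contrast between 0 and 4.2 in the same direction changes sign under B.

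**An example with assumed values (start/end of clamp, FMD %).** HiEx + metformin goes from 5/6 to 6/7.5: A = +1.5, B = +0.5. LoEx + metformin goes from 5/6 to 8/8.5: A = +2.5, B = −0.5. LoEx is better by 1.0 under A and worse by 1.0 under B.

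**How often a reversal would be significant.** Two assumptions are needed that the documents do not supply: the end-clamp change also has SD 3.4, and it correlates rho with the basal change. Then SD(B) = 3.4 × √(2(1 − rho)). The table takes the end-clamp contrast as exactly zero, so that the whole basal contrast appears in B with the opposite sign.

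| rho | SD(B) | significant B, basal contrast 4.2 | significant B, basal contrast 2 |
|---|---|---|---|
| 0.3 | 4.02 | 52% | 9% |
| 0.5 | 3.40 | 70% | 13% |
| 0.7 | 2.63 | 93% | 25% |

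Conversely, if the basal contrast is 4.2 and insulin adds the same amount in both arms, end-clamp FMD is significant in 70% of trials and the increment in 0.8%, its nominal level. In that setting the increment gives the right answer to the question of what insulin adds.

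**Which reading the text supports.** Section 1.3 D is the endpoint definition and speaks of insulin's influence on FMD. With one FMD reading before insulin and one after, that is a within-visit difference. The remark in section 1.2 describes what earlier studies lacked and defines no endpoint. Section 1.3 D names FMD and not the ultrasound measure.

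**Whether the ANOVA can take it.** One end-minus-start score per visit gives each subject a pre and a post value, which is what a group-by-test model needs. Its interaction term is the same test as group by test by clamp stage in a three-way model. The absent clamp-stage factor is therefore not a separate fault.

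**The case for a change.** The best case for acting is that a natural reading is not a pre-specified one. The vascular quantity carries half of the main hypothesis and also enters the planned correlations with glycemic control and blood pressure. Section 6.1, where a formula might be expected, holds only its template instruction. One sentence would close the gap, and section 4.3 shows that the project is already under way.

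Part of this stands. The formula is not written, and the identity above shows that the two readings can disagree in exactly the situation the trial hopes to find. But the sentence would only record the definition that an analyst following section 1.3 D would use anyway. It adds no measurement, model or alpha. The risk of a later switch is a possibility only: nothing in the documents shows that a reading was chosen after outcomes were seen.

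The demand for a both-or-either rule does not stand. Section 1.2 frames the proposal as metabolic and/or vascular, and section 1.3 D wants the two measures in order to separate vascular from metabolic effects. A split result would be informative. Requiring both would bring co-primary logic to two secondary outcomes. If each had 80% power, joint success would occur in 64% of trials for independent outcomes (0.80 × 0.80) and 73% at a correlation of 0.8, a loss of 7 to 16 points.

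**Conclusion.** No change to the plan is called for. Section 1.3 D leaves a detail unwritten that analysts would fill sensibly: end-clamp minus pre-clamp FMD at the same visit, entered as one value per visit in the group-by-test ANOVA of section 1.6.

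The 52% to 93% reversal is an extreme illustration. It needs a basal contrast of 4.2 points, an end-clamp contrast of zero, an end-clamp SD equal to the basal one, and rho between 0.3 and 0.7. At a 2-point basal contrast it is 9% to 25%.

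Anyone interpreting the increment should look at basal and end-clamp FMD by arm beside it, since the increment contrast is the end-clamp contrast less the primary one. Both components are collected. The primary outcome, its sample size and its analysis do not depend on this point.

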1.4 Preliminary Data

We do have not have preliminary data on endothelial function with metformin combined with exercise. However, our preliminary work in Met/prediabetic individuals shows that when metformin is combined with HiEx there tends to be a blunting effect on skeletal muscle metabolic insulin resistance ^{4,5,33}. Furthermore, we previously showed that metformin blunted HiEx-induced improvements in blood pressure and hs-CRP vs. HiEx only. Together, along with literature from other investigators, it reasons endothelial function may be impacted by metformin plus exercise.

1.5 Sample Size Justification

The primary outcome for this study will be changes of basal flow mediated dilation (FMD) before the insulin clamp pre and post intervention. Based on our prior work 47, with 15 subjects per treatment arm we expect to have at least an 80% chance of rejecting the null hypothesis that the mean pre to post-exercise change in FMD is the same for any pair of treatments if the true means of the underlying distributions differ by more than 4.2%. Details: In computing the minimum detectable effect size of 4.2%, we assumed that the measurements for pre to post-treatment change in FMD will be normally distributed and that the measurement variability in the pre to postexercise FMD changes is the same regardless of the treatment. Moreover, we assumed that the standard deviation of the underlying distributions is 3.4% based on our prior work 47, which is notably larger than reported in the metformin literature 48. To account for a total of 6 pairwise between-treatment comparisons, a Bonferroni corrected experiment-wise type I error of 0.05 was utilized to derive the minimum detectable between-treatment difference of 4.2%. Limitations: We do not have data from the literature or from our own studies with exercise to estimate power on changes in MBV, nor with the combination of exercise+metformin. However, considering MBV, we based our estimate of sample size on our study examining the effect of insulin on MBV in both skeletal and cardiac muscle in the control setting and in the setting of elevated plasma FFA. We observed that insulin significantly increased microvascular blood volume (MBV) at both sites (p<0.01) in the absence of elevated FFA and this effect was entirely blocked by elevating plasma FFA. These observations were made in 22 subjects, although less would have yielded significance ^{36, 42}. Moreover, previous work that we conducted with HiEx+metformin demonstrated significant blunting effects on systolic blood pressure vs. exercise alone with only 8 people per group 5. Anticipated dropout: Based on our prior work with this study population, we anticipate that the study participant dropout rate will be 10-15%. Therefore, we intend to enroll 80 subjects with 20 subjects randomized to each treatment intervention.

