1.6 Study Variables

A. Independent Variables, Interventions, or Predictor Variables

This is a randomized by sex, double-blind, placebo controlled trial. A placebo is needed to minimize potential behavioral changes with pharmacological intervention. This will isolate the effects of exercise intensity based training on respective outcomes. As a result, exercise at low or high intensity with placebo will serve as standard of care/control, while exercise at low or high intensity with metformin will be the experimental conditions. Pre and post test data will be compared statistically.

Data will be analyzed using R (Vienna, Austria, 2011). A two-way repeated measures analysis of variance (ANOVA) will be used to assess time course differences (group x test). Bonferonni post-hoc analysis will be used to determine group differences and paired t-tests will be used to assess within treatment effects. Linear regression analyses will be used to identify relationships between respective variables. A *P*<0.05 will be considered statistically significant. Data will be expressed as mean ± SEM.

12/31/2499

The same statistical approach for secondary analysis will be conducted as the primary variable analysis.

B. Dependent Variables or Outcome Measures

- 1. Insulin Sensitivity
- 2. Fitness (e.g. VO2max, physical activity amount, heart rate, RPE, etc.)
- 3. Body composition (e.g. weight, fat, FFM, BMD, waist circumference, etc.)
- 4. Vascular Function (e.g. FMD, CEU, heart, arterial stiffness, etc.)
- 5. Questionnaires (e.g. Sleep, activity, quality of life, hunger, etc.)
- 6. Glucose (e.g. substrate, isotope)
- 7. Lipid Profile (e.g. TG. HDL. FFA. etc.)
- 8. Blood clinical chemistries (e.g. CBC)
- 9. C-peptide
- 10. Insulin
- 11. Inflammation (e.g. endothelin-1, adiponectin, Microparticles, etc.)
- 12. Nitrates
- 13. Gut hormones (e.g. ghrelin, GLP-1, etc.)
- 14. Pregnancy (in females), blood for screening at each admission.
- 15. Energy metabolism (e.g. rest, exercise, insulin-stimulation).
- 16. Gut microbiota
- 17. Cognitive measures using NIH toolbox

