4.3 Number of Subjects

A. Total Number of Subjects

12/31/2499

Based on prior work by our group, we anticipate that approximately 25% of subjects who enroll in the study will withdraw/drop out early. Currently the study requires 45 people of 80 given it is a transfer project when our team was at the University of Virginia. In addition, we expect that 70% of individuals who we screen/consent will not qualify. **Thus, we expect to screen 225 subjects of whom about 67 will participate and 45 will complete the study.**

B. Total Number of Subjects If Multicenter Study

NA

C. Feasibility

We are confident that we can recruit the required number of health volunteers given the population in and surrounding Rutgers University. We are also confident we can recruit patients with risk factors for metabolic syndrome in the Clinical Academic Building at RWJMS.

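### Stated power for the primary outcome (80% for a 4.2-point FMD difference at 15 per arm) is about 74% under a two-sided Bonferroni test; sidedness and formula are not given

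*Combined protocol and SAP*

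**What the plan says.** Section 1.5 (Sample Size Justification) states that "with 15 subjects per treatment arm we expect to have at least an 80% chance of rejecting the null hypothesis" of equal mean pre-to-post FMD change for any pair of treatments, provided the true means differ by more than 4.2 points. Its assumptions are normality, an SD ("we assumed that the standard deviation of the underlying distributions is 3.4" points) and equal variance in all arms ("the measurement variability in the pre to postexercise FMD changes is the same regardless of the treatment"). For the six pairwise comparisons, "a Bonferroni corrected experiment-wise type I error of 0.05 was utilized to derive the minimum detectable between-treatment difference of 4.2" points. The section then says that "we anticipate that the study participant dropout rate will be 10-15" percent and sets enrolment at 80, with 20 randomized to each arm.

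Section 1.6 (Study Variables) gives the analysis: a two-way repeated measures ANOVA (group by test), after which "Bonferonni post-hoc analysis will be used to determine group differences", with significance at P<0.05. Neither section states the sidedness of the pairwise tests or the power formula.

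On attrition, section 4.3 (Number of Subjects) differs from section 1.5: "we anticipate that approximately 25% of subjects who enroll in the study will withdraw/drop out early", and "we expect to screen 225 subjects of whom about 67 will participate and 45 will complete the study".

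**The concern.** Section 1.5 gives every input needed to recompute its claim except sidedness and formula. With the usual two-sided test at 0.05/6 per pair, those inputs do not give 80% power at 4.2 points.

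This is the only power statement for the primary outcome. Someone interpreting a non-significant pair would take the chance of missing a true 4.2-point difference to be at most 20%. At the sample size named, it is about 26% (23 to 30% depending on formula). With small arms and six corrected comparisons, non-significant pairs are likely to need interpretation.

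**Working it through.** **Inputs, all from section 1.5.** n = 15 per arm; SD of change = 3.4; difference = 4.2; six pairs; experiment-wise error 0.05, so 0.05/6 = 0.00833 per pair; equal variance in the four arms.

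**Standard error and noncentrality.**
- SE = 3.4 × √(2/15) = 1.2415
- Noncentrality = 4.2 / 1.2415 = 3.383

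**Formulas.** Power = P(T > c), where T is noncentral t with the noncentrality above and c is the critical value. The normal version is Φ(3.383 − z), with detectable difference (z + 0.842) × SE. The t-based detectable difference is the value at which noncentral t power equals 80%. Degrees of freedom are 2 × 15 − 2 = 28 for a two-sample t, or 4 × 15 − 4 = 56 with the error term pooled over four arms. The pooled version fits the plan best: section 1.5 assumes equal variance, and with two time points the group-by-test interaction is an ANOVA on the change.

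**Trying to reproduce the plan's figure at 15 per arm.**

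| Test at 0.05/6 | Critical value | Power at 4.2 | Difference detectable with 80% power |
|---|---|---|---|
| Two-sided, pooled (df 56) | 2.735 | 73.9% | 4.46 |
| Two-sided, two-sample t (df 28) | 2.839 | 70.3% | 4.61 |
| Two-sided, normal | 2.638 | 77.2% | 4.32 |
| One-sided, pooled (df 56) | 2.468 | 81.6% | 4.12 |
| One-sided, two-sample t (df 28) | 2.546 | 79.2% | 4.24 |
| One-sided, normal | 2.394 | 83.9% | 4.02 |

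No two-sided version reaches 80% or gives 4.2. A simulation of 200,000 trials gave the same two-sided t powers (73.9% pooled, 70.3% two-sample). The one-sided two-sample t gives 4.24, which rounds to 4.2. One-sided 0.05/6 has the same critical value as two-sided 0.05/3, so a divisor of three instead of six would produce the same number.

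**Other multiplicity methods, two-sided.** Šidák gives 70.6% (two-sample) or 74.1% (pooled), and Tukey gives 76.6%. With no adjustment, the two-sample t gives 90.4%.

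**Rounding.** With the values most favourable to the plan (difference 4.25, SD 3.35), the two-sided figures are 73.2% (two-sample), 76.7% (pooled) and 79.8% (normal). All stay below 80%.

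**SD that would give 80% at 4.2 with 15 per arm, two-sided.** 3.20 (pooled) or 3.10 (two-sample), against the stated 3.4.

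**At the planned enrolment.** Completers per arm are 20 × 0.85 = 17 and 20 × 0.90 = 18 under section 1.5, and 20 × 0.75 = 15 under the 25% in section 4.3.

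| Completers per arm | Two-sided power at 4.2: two-sample t / pooled | Detectable difference: two-sample t / pooled |
|---|---|---|
| 15 | 70.3% / 73.9% | 4.61 / 4.46 |
| 17 | 77.8% / 80.6% | 4.29 / 4.17 |
| 18 | 81.0% / 83.5% | 4.16 / 4.05 |

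The smallest n per arm with 80% two-sided power at 4.2 is 17 (pooled), 18 (two-sample) or 16 (normal).

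**The case against.** The strongest reply is that the documents never say two-sided. With a one-sided 0.05/6 test the printed 4.2 is essentially recovered, and section 1.1 does state directional hypotheses for some contrasts. On this view the certain defect is an unreported assumption, not a miscalculation. It is true that only the investigators know what was run. But a one-sided test does not fit the equality null for any pair, the ANOVA with Bonferroni post-hoc tests, or the fact that section 1.1 gives no direction for all six pairs. The one-sided two-sample version also gives 79.2%, just under the claim.

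A second reply is that 4.2 may come from a different n. Two-sided detectable differences of 4.18 (16 per arm, normal), 4.17 (17, pooled) and 4.16 (18, two-sample t) all round to 4.2. That is possible, but the text ties the claim to 15, so the sentence would still need correcting.

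A third reply is that the practical effect is small. The trial randomizes 20 per arm, and with 10-15% dropout two-sided t power is 78-83%. The detectable difference at 15 moves by only about 6% (4.46 / 4.2 = 1.06), and an SD of 3.2 would close the gap on the pooled formula. This stands, and it limits the seriousness of the point. It relies, however, on the dropout rate in section 1.5. At the 25% in section 4.3, the trial returns to 15 per arm and about 74%.

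**Conclusion.** The claim of at least 80% power at 4.2 points with 15 per arm does not hold under any two-sided formula. Power is 74% pooled (range 70-77%), and the detectable difference is 4.46 pooled (range 4.32 to 4.61), so 4.2 is low by about 0.26 points on the pooled formula. This rests on section 1.5's own SD, equal variances and six-fold Bonferroni correction, and on reading the tests as two-sided, which the plan implies but does not state. If one-sided tests were intended, the figure is approximately right but neither declared nor justified. Section 1.5 should be corrected in either case. The shortfall is one to three subjects per arm and does not undermine the design.

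**What to change.** In section 1.5, state the sidedness (two-sided, to match section 1.6) and name the formula. Then choose one of the following:

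- **(a) Keep 15 completers per arm.** Give the detectable difference as about 4.5 points (4.6 by two-sample t), or power at 4.2 as about 70-74%.
- **(b) Base the claim on the planned enrolment.** With 17 to 18 completers per arm, two-sided t power at 4.2 is 78-83%. Both counts exceed 80% on the pooled formula; only 18 does by two-sample t. This first requires the 10-15% dropout in section 1.5 to be reconciled with the roughly 25% in section 4.3, whose own counts imply 1 − 45/67 = 33%.

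If a one-sided test was intended, say so and justify it for all six pairs.

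The cost is one paragraph of wording. No extra patients are needed and the six comparisons stay as they are. Under (a), the published figure becomes slightly less favourable.
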